1. BACKGROUND AND RATIONALE

Prevalence of overweight and obesity amongst Singaporean adolescents has increased from 11 to 12 per cent in 2014 in school children (1) Current numbers of adolescents who are overweight or obese are predicted increase to 148,000 in year 2025. Adolescents who are overweight or obese have a moderate to substantial risk of remaining so in adulthood and they suffer from a range of immediate and long term medical and psychosocial complications. (2, 3) In addition, obesity-related cardiovascular disease risk markers present in adolescence are predictive of obesity related morbidity present in adulthood. (4). Importantly, obese and overweight adolescents who became normal weight adults, had cardiovascular disease risk markers that were similar to those of persons who had a normal BMI consistently from childhood to adulthood (5) Overweight and obese adolescents aged 12-15 were also found to have a higher chance of having normal Body Mass Index (BMI) at adulthood compared to children and adolescents of other age groups. (5) This further highlights a golden opportunity for intervention in adolescent obesity. Adolescent obesity is also a costly chronic disease and the lifetime direct medical costs is estimated to cost S\$24,000 more per adolescent relative to a normal weight child. (6) Indirect costs of obesity such as carer's loss of productivity and intangible costs such as loss of well-being further add to the burden of adolescent obesity.

The Expert Committee on the Assessment, Prevention and Treatment of Child and Adolescent Overweight and Obesity(7) recommends a staged based approach to the management of adolescents with overweight and obesity from Stage 1-4 with increasing intensity of management in higher stages. Stage 3 is recommended for overweight and obese adolescents that showed poor response to Stage 1 and 2 or for adolescents with BMI of greater than 99th percentile. These adolescents are termed high risk obesity in our WMC program. Stage 3 interventions consist of multidisciplinary visits with frequent (up to weekly) visits for 8 or more weeks.

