Several studies in adolescent obesity have consistently identified early treatment engagement as evidenced by attendance and initial weight loss, between 4-10 weeks, to be strongly predictive of long term weight loss (9, 26, 27). Early responders have been reported in studies varying from 60-80% (9, 27). These data support the hypothesis that a large proportion of obese adolescents can be managed in primary care with structured interventions. Identification of early treatment attendance and initial weight loss introduces a second filter to Stage 3 program. A third filter will be the identification of the severely obese adolescents as severely obese adolescents have been found to have higher risks of obesity related co-morbidities (7) with poor response to treatment (28). Early responders, who are not severely obese, can then be channelled to low risk WMC clinics which are made to simulate a primary care provider clinic with only 10-15 minutes consultation time. If the low risk clinics are found to be successful, it has potential to be implemented widely in primary care. To our knowledge, there have been no clinical program that have utilized a waitlist intervention to identify early responders in WMC as a triage approach.

We thus propose a waitlist intervention with two main components of a brief intervention by a nurse coordinator followed by the Kurbo program to identify early responders, who are not severely obese, in our WMC waitlist system. The waitlist intervention is cost effective and makes only very modest demands on the nurse clinician's time and skills, which is a strategy we have chosen deliberately. If successful, it can be implemented widely as a brief opportunistic intervention and increase the degree to which primary care providers (polyclinic nurses and doctors, general practitioners or school health services) engage with adolescent obesity interventions.

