2. HYPOTHESIS AND OBJECTIVES

Primary objective will be to examine the proportion of patients triaged to the low risk WMC clinics after brief intervention by a nurse coordination and completion of 4 sessions of Kurbo Program over a 12 month recruitment period.

Secondary objectives:

1. To examine the effect of the waitlist intervention and WMC intervention on mean BMI z-score change at 3 months and 6 months.
2. To examine the feasibility of using Kurbo program as a waitlist intervention for the target population as measured by quantifying the percentage of patients offered the program who agreed to enrol.
3. To examine program fidelity as measured by the percentage of patients who complete each of the 12 sessions of online coaching by Kurbo coaches
4. To examine changes in treatment outcomes as a function of program fidelity as measured by those who complete more online coaching show greater improvements in BMI z-score
5. To examine other factors that predict poor response (parental BMI, quality of life, disordered eating and physical activity measurement) in high risk WMC
6. To examine the effects of waitlist intervention on lifestyle changes (nutrition and physical activity), quality of life and disordered eating at 3 and 6 months.
7. To examine the rate of attrition from WMC after implementation of the waitlist intervention and new model of care in WMC.
8. Examine changes in branched chain amino acid(BCAA), aromatic amino acid (AAA) and long chain acylcarnitines, insulin and second hour glucose results and fasting lipids at baseline and at month 6.

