4.3. Inclusion Criteria

Subject must meet all of the inclusion criteria to participate in this study.

- a. Overweight as defined by BMI percentile of above 90th percentile
- b. Age 10-17 years old in the year of referral
- c. Ability to provide informed consent
- d. Adolescents with a phone which is able to download the application to be used on their devices

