5. STUDY DESIGN AND PROCEDURES/METHODOLOGY

Children aged 10-17 years old with BMI percentile of above 90th percentile, who are referred to the WMC, will receive a brief intervention by the WMC nurse coordinator followed by introduction to Kurbo program for more detailed dietary and physical activity recommendations and implementation of behavioural changes. The patient's progress will be reviewed by the nurse clinician at one month post intervention to determine whether the BMI percentile has shown a reduction through the Kurbo Program. Patients that declined Kurbo intervention, has a BMI of more than 99th percentile or continue to have increase in their BMI percentile in Kurbo program, will be offered the high risk weight management clinic appointment for a more detailed multidisciplinary evaluation for targeted intervention. Patients that are able to engage with Kurbo intervention and showed a decrease in BMI percentile over 4 sessions of Kurbo will be offered the low risk weight management clinic.

The following section illustrates how and when the outcomes will be measured. Figure 1 depicts the flow diagram for an adolescent at the point of referral to the WMC.

Figure 1: Flow diagram of the intervention at the point of referral to WMC

Study visits and procedures

The expected duration of study involvement for each participant will be 6 months with 5 in-person visits with the study team. Table 1 depicts the study visits and measurements for each visit.

Table 1: Study visits and measurements

	Baseline	Visit 1	Visit 2	Visit 3	Visit 4	Visit 5
Parental demographics and parental BMI	x					
Anthropometry (weight, height, waist circumference, blood pressure and body fat composition)	x		x	x		x
Peds QL questionnaire	x			x		x
Three day food diary	x			x		x
Eating Pattern Inventory	x			x		x
Evaluation questionnaire				x		
Accelerometry	x			x	x	
Fasting insulin, lipids, oral glucose tolerance test		x			x	
Plasma amino acid, long chain acylcarnitine levels and vitamin D level, calcium, magnesium, phosphate and alkaline phosphatase		x			x	

First contact (Baseline):

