Prior to the clinic visit, the nurse coordinator or clinical research coordinator will obtain a summary of the adolescent's progress in Kurbo to aid the discussion during the clinic visit. If there has been no change in the adolescent's BMI percentile after 4 sessions of Kurbo program or the adolescent had not signed up for Kurbo, the adolescent will be placed in the high risk clinic. If the adolescent had shown reduction in BMI percentile after 4 sessions of Kurbo, they will be placed in the low risk clinic. There are several key objectives to the visit. Firstly, it is to objectively measure the patient's weight and height, body fat composition, waist circumference and blood pressure. In the low risk clinic, the current clinic slots are in 15 minutes slot as the main purpose of the consult is to screen for obesity related co-morbidities and for motivational interviewing. The visit also allows the nurse coordinator to build further rapport with the adolescent. In the high risk clinic, the clinic slots are in 30 minutes slot to allow for more time to obtain a medical and psychosocial history. The weight management program for high risk and low risk WMC will be as routine care.

Current low risk WMC patients will be offered 2 monthly follow up with optional dietitian and exercise physiologists counselling and exercise sessions. The high risk WMC patients will be routinely offered the standard high risk follow up protocol consisting of weekly follow up with the multidisciplinary team for 4 weeks followed by 2 weekly appointments for 2 months and monthly appointment thereafter based on clinical response.

Visit 3:(12-23 weeks)

Prior to the clinic visit, the nurse coordinator or clinical research coordinator will obtain a summary of the adolescent's progress in Kurbo to aid the discussion during the clinic visit. The follow up will be timed together with the WMC appointment to measure the patient's weight and height, body fat composition, waist circumference and blood pressure as well as administration of the questionnaire. Accelerometers may also be fitted or returned to

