8.2. Statistical and Analytical Plans

Data will be analysed using SAS version 9.3 for Windows (SAS, Inc., Cary, NC USA). BMI will be calculated as kg/m² and BMI-z score calculated using the L, M, S parameters published by the CDC. (34) Baseline demographic, anthropometric measurements, parental BMI, quality of life measurement, disordered eating and physical activity were compared between those in low risk WMC versus those in high risk WMC using the Wilcoxon rank-sum test and the two-sample-t-test for non-normal and normal continuous variables, respectively, and the Fisher's exact test for categorical variables. Changes in cardiometabolic risk factors between first visit and at month 12 will be compared using the paired-sample t-test. Generalized linear mixed model will be carried out on the BMI z-score over multiple visits over 12 month follow up period. The mean value of BMI z-score is considered as a function of time from the baseline. The variance components is used as the covariance structure in generalized linear mixed model. It models a different variance component for each random intercept to allow each child to have his/her own overall level of BMI z-score after taking into account baseline covariate. A time-group interaction will be included to test whether the rate of change of BMI z-score is different between adolescents in low risk and high risk WMC.

There is no reason to assume that this project will lead to an excess of adverse events as the waitlist intervention consists of advice from the nurse and offer of referral to a Kurbo program, neither of which seem likely to create harm. Nonetheless, there are several safety net in place for the waitlist intervention. Firstly, as part of standard Kurbo procedures, any excessive weight loss or weight gain will prompt the Kurbo coaches to inform parents to seek help from their GP and the WMC nurse coordinator will be informed if any concerns arise. Secondly, the WMC nurse coordinator will have administrative rights to Kurbo program and will be able to monitor patient's weight data and communication with Kurbo coaches and will highlight any concerns that arise as a result of intervention. There will also be a feedback form (A month 3 evaluation) administered by the clinical research coordinator on the participants' attitudes to the waitlist intervention and to identify any adverse events at the first WMC visit. As this is a pilot study, there will be no interim analyses.

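### The low risk placement rule leaves out the above-99th-percentile exclusion, so a responder above that cutoff is low risk under one sentence and high risk under another

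*Combined protocol and SAP*

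**What the plan says.** Section 5 states the triage rule twice.

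- **Opening paragraph, high risk.** A patient who declined Kurbo, or who "has a BMI of more than 99th percentile or continue to have increase in their BMI percentile in Kurbo program", is offered the high risk clinic. The conditions are joined by *or*, so a BMI above the 99th percentile is enough alone.
- **Opening paragraph, low risk.** The next sentence says that patients who engage and "showed a decrease in BMI percentile over 4 sessions of Kurbo will be offered the low risk weight management clinic". It has no BMI ceiling.
- **Visit 2.** "If the adolescent had shown reduction in BMI percentile after 4 sessions of Kurbo, they will be placed in the low risk clinic". The high risk triggers listed there are an unchanged BMI percentile and not having signed up for Kurbo. The 99th percentile is not among them.

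Section 1 gives the intent. Of adolescents who respond poorly to the earlier stages, or whose BMI is above the 99th percentile, it says: "These adolescents are termed high risk obesity in our WMC program". It treats severe obesity as a filter additional to early response: "Early responders, who are not severely obese, can then be channelled to low risk WMC clinics".

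The only BMI criterion for entry (Section 4.3) is "Overweight as defined by BMI percentile of above 90th percentile". The primary objective (Section 2) concerns this quantity: "proportion of patients triaged to the low risk WMC clinics after brief intervention by a nurse coordination and completion of 4 sessions of Kurbo Program". Section 8.2 uses the same two clinics as groups, with a time-by-group interaction to "test whether the rate of change of BMI z-score is different between adolescents in low risk and high risk WMC".

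**The concern.** An adolescent who starts above the 99th percentile, completes four sessions, and shows a lower percentile that is still above the 99th satisfies both rules in Section 5. Staff working from the Visit 2 text alone would never meet the exclusion.

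Three things depend on which sentence is applied:

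- **The primary proportion**, which is a count of low risk placements.
- **The group comparisons in Section 8.2.** Section 1 says severely obese adolescents respond poorly to treatment, so moving them between groups can change the contrast in BMI z-score slopes.
- **Care.** The high risk clinic offers much denser follow-up, and Section 1 describes severely obese adolescents as having more obesity-related comorbidity.

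**Working it through.** The plan states no figure for the primary proportion and has no sample size calculation (Section 8.1), so there is nothing to reproduce. The check compares the rules, then sizes the gap between them.

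**1. The conflict case**

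| Rule | Placement of a responder still above the 99th percentile |
|---|---|
| Section 5 opening, high risk sentence | High risk |
| Section 5 opening, low risk sentence | Low risk |
| Section 5, Visit 2 | Low risk |
| Section 1, intent | High risk |

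The last row takes severely obese to mean above the 99th percentile. That is an inference, because the documents do not define the term. The first three rows conflict without it.

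**2. Can the case arise?** Section 4.3 sets no upper limit, and Section 1 describes referrals as extending to severe obesity. The judging visit is not stated outright; the one-month or Visit 2 review is the natural reading. Judging then, and not at baseline, removes few cases:

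- The 99th percentile is z = 2.33.
- The local Kurbo pilot in Section 1 reports a mean fall of 0.26 in BMI z-score over 3 months. With that full fall, only a child starting below 2.33 + 0.26 = 2.59 (99.5th percentile) drops under the cutoff.
- Assuming a linear fall, 4 of 12 sessions give 0.26/3 = 0.087. Only a child starting below about 2.41 (99.2nd percentile) drops under it.

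**3. Effect on the primary proportion.** Take 45 as the denominator (Sections 4.1 and 8.1). Let q be the share above the 99th percentile and r the response rate in that group. Both are assumptions.

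- Per child: 1/45 = 2.2 points.
- Total shift = q × r; children affected = 45 × q × r.

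| q | r = 30% | r = 40% | r = 80% |
|---|---|---|---|
| 10% | 3 points (1.4 children) | 4 (1.8) | 8 (3.6) |
| 20% | 6 (2.7) | 8 (3.6) | 16 (7.2) |
| 40% | 12 (5.4) | 16 (7.2) | 32 (14.4) |

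Section 1 cites early response of 60–80% overall but poor response in severe obesity, so the first two columns are the more plausible.

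Example: q = 20%, response 30% above the cutoff and 60% at or below it.

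- Without the exclusion: 0.2 × 0.3 + 0.8 × 0.6 = 0.54.
- With it: 0.8 × 0.6 = 0.48.
- 95% half-width at 0.48: 1.96 × √(0.48 × 0.52/45) = 0.146, about 15 points.

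**4. Effect on scheduled clinic contacts in 12 weeks** (schedules in Section 5, Visit 2)

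- High risk: weekly for 4 weeks, then every 2 weeks for 2 months: 4 + 8/2 = 8.
- Low risk: every 2 months: about 1.

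**The case against.** The strongest reply is that the intended rule can be recovered. Section 1 limits the low risk clinic to responders who are not severely obese. The opening paragraph of Section 5 can be read in order, with the first sentence removing those above the 99th percentile and the second placing the remainder; Visit 2 is then a summary. Figure 1, the flow diagram, is missing from the text available here and may show the order. If staff apply the intended rule, the shift is zero. This is a fair account of intent, and it is why the repair is small. It does not remove the conflict: Visit 2 lists its own triggers for both clinics, and a primary endpoint should not depend on background rationale overriding the procedure.

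Other points stand in part:

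- **Size.** The range reflects the assumed q and r, and the 32-point end needs a high response that Section 1 makes unlikely.
- **Denominator.** The 2.2 points per child rests on all 45 being counted. The primary objective mentions completion of four sessions, so a completers-only denominator is possible; a smaller denominator makes each child count for more.
- **Care.** The 8-to-1 contrast counts clinic appointments only. Kurbo coaching runs to week 12 in both groups, and low risk patients have optional dietitian and exercise sessions.
- **Weight of the result.** This is a single-centre pilot with no success threshold, and the Section 8.2 groups are not randomised. The proportion is still its main result.

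**Conclusion.** The concern holds. As written, the Visit 2 rule places a responder above the 99th percentile in the low risk clinic, against the high risk sentence of Section 5 and the intent in Section 1. The text of the plan does not say which prevails. This rests on the wording alone, since Figure 1 could not be seen.

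The likely shift in the primary proportion is 3 to 16 points, assuming 10 to 40% of participants are above the 99th percentile and 30 to 40% of those respond. At its upper end it is about as large as the 95% half-width of the estimate. If percentiles are recorded as whole numbers (the precision is not stated), some of these children would show no change and the shift would be smaller. It should be corrected, but it does not threaten the study as a whole.

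**What to change.** - Add *and BMI is not above the 99th percentile* to the low risk rule in both places in Section 5, and add a BMI above the 99th percentile to the Visit 2 list of high risk triggers.
- Name the visit at which the cutoff is judged. The one-month or Visit 2 review fits the present text best.
- Use that single wording to define the primary endpoint and the low and high risk groups in Section 8.2.
- Report the primary proportion also by baseline 99th-percentile status, so that readers can see how much the exclusion contributes. This is useful but not needed to resolve the conflict.
- As tidying only, list no change and increase together under high risk. This does not alter the primary count.

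The cost is a wording amendment and one extra row in the primary table. Weight and height are already measured at baseline and Visit 2.

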6. SAFETY MEASUREMENTS

6.1. Definitions

Serious adverse event (SAE) in relation to human biomedical research, means any untoward medical occurrence as a result of any human biomedical research which:

- results in or contributes to death
- is life-threatening
- requires in-patient hospitalisation or prolongation of existing hospitalisation
- results in or contributes to persistent or significant disability/incapacity or
- results in or contributes to a congenital anomaly/birth defect
- results in such other events as may be prescribed

6.2. Collecting, Recording and Reporting of Serious Adverse Events to CIRB

Reporting of adverse events involves the Principal Investigator submitting to CIRB the SAE Reporting Form to CIRB within the stipulated timeframe. The Principal Investigator is responsible for informing the institution representative, the chairman medical board (when required by the institution for local SAE resulting in death), sponsor or regulatory bodies as required and appropriate.

Reporting timeline to CIRB:

Severity:	Nature:	Reporting Requirement:	Form to use:
Local SAE -resulting in death[#]	Unexpected/ Expected	Report within 24 hours*.	LSAE Report Form
Local SAE – life-threatening	Unexpected/ Expected		
Local SAE – not life-threatening	Unexpected	Report as soon as possible but not later than 7 calendar days*.	LSAE Report Form
Local SAE – not life-threatening^{**}	Expected		
Non-local^{***} SAE – fatal or life threatening	Unexpected	Report within 30 calendar days. Submit through Other Reportable Event Form.	Available format (e.g. CIOMS)

Only related SAE (definitely / probably / possibly) need to be reported to CIRB. Unrelated SAE do not need to be reported to CIRB. Related means there is a reasonable possibility that the event may have been caused by the procedures involved in the research.

6.3. Safety Monitoring Plan

As this is an unblinded study with no substantial risk, the Principal investigators, together with the Co-Investigators and research coordinators, who are responsible for the day-to-day management of the trial, will ensure that the research methodology is adhered to and that appropriate action is taken to ensure to safeguard participants and the quality of the trial itself. They will also meet at least quarterly throughout the course of the trial. Data entered by the clinical research coordinator will be counter checked by the investigators to ensure that the data correlates with the case report forms.

6.4. Complaint Handling

Complaints will be handled as per the Hospital's policy on handling patients' complaints.

7. DATA ANALYSIS

7.1. Data Quality Assurance

The clinical research coordinator will ensure that the data entry forms are completed. The data entry forms will be counter checked by the investigators to ensure that the data obtained is accurate and reliable.

